#### 12.3. Best objective response

- CR: one objective status of CR documented before relapse
- PR: one objective status of PR documented before progression but not qualifying as a CR

- Stable: at least one objective status of stable disease documented at least 6 weeks after registration, no qualifying as a CR or PR
- Increasing disease: objective status of progression within 12 weeks of registration not qualifying as CR, PR or SD
- Inadequate assessment, response unknown: progression greater than 12 weeks after registration and no other response category applies

# 13.0 CRITERIA FOR REMOVAL FROM STUDY

### 13.1. Criterial for premature patient removal from study

Patients may voluntarily withdraw from the study or be removed from the study at the discretion of the investigator at any time. Patients may be withdrawn from the study if any of the following occur:

- Progressive disease
- Unacceptable toxicities
- Protocol deviation
- Lost to follow-up
- Pregnancy
- Discovery of patient ineligibility
- Errors in treatment compliance
- Administrative problems

In addition to the general study treatment withdrawal criteria, the following study specific criteria will also require premature study treatment discontinuation:

- Study treatment modifications that result in discontinuation
- Interruption of mocetinostat treatment for more than 21 days
- Use of prohibited medication
- Start of any other anti-neoplastic therapy

If a study treatment withdrawal occurs, or if the patient fails to return for visits, the investigator must determine the primary reason for a patient's premature withdrawal from study treatment and record this information in CRDB. In case of withdrawal from study treatment, the patient needs to indicate on the informed consent form whether she is willing to continue with subsequent follow-up procedures

### 13.2. Patient Followup

Patients lost to follow up should be recorded as such in CRDB. For patients who are lost to followup, the investigator should show "due diligence" by documenting in the source documents steps taken to contact the patient, e.g., dates of telephone calls, registered letters, etc.

### 13.2.1. Safety followup

All patients will be followed for adverse events and serious adverse events for at least 30 days following the last dose of mocetinostat. At the end of this period (between day 30 and day 37 after

last dose), the investigator should contact the patient to inquire about any AE observed/concomitant medication taken during this period. This could be done via either an office visit or a phone contact.

Patients whose treatment is interrupted or permanently discontinued due to an adverse event or abnormal laboratory value must be followed until resolution or stabilization of the event, whichever comes first. In case the patient has any abnormal lab values at end of treatment that are considered clinically significant by the investigator, the patient needs to come to the site for repeat blood analysis until resolution or stabilization including at least a site visit with respective analyses 30-37 days after end of treatment.

If patients refuse to return for safety evaluation visits or are unable to do so, every effort should be made to contact them by telephone to determine their status. Attempts to contact the patient should be documented in the source documents (e.g., dates of telephone calls, registered letters, etc.).

### 13.2.2. Efficacy followup

Patients who discontinue study treatment for reasons other than disease progression, death start of new anti-neoplastic therapies, lost to follow-up, or withdrawal of consent to efficacy follow-up will continue to have radiological tumor assessments per Table 10-1 after end of treatment, or until disease progression, start of a new antineoplastic therapy, death, lost to follow-up, or withdrawn consent.

At the time the patient discontinues the efficacy follow-up period or starts a new antineoplastic therapy, this will be recorded in CRDB.

### 14.0 BIOSTATISTICS

The primary objective is to determine the efficacy of Mocetinostat in patients with relapsed/refractory DLBCL and FL who have inactivating mutations of acetyltransferase genes. To this end we will examine the endpoint of 1-yr overall response (complete response or partial response defined as per Cheson criteria further elaborated in Section 12.1). Currently this rate is around 15% for both lymphoma subtypes based on a previous study [2], and we expect to improve it to 40%. To this end we will use two parallel optimal Simon two-stage designs, one for each subtype, to test the rate of 15% (lower than which will be unacceptable) vs 40% (higher than which will be acceptable). For each subtype, in the first stage, we will enroll 10 eligible patients. If 1 or 0 patients show response in a year, no additional patients will be enrolled and the regimen will be considered not promising. If 2 or more patients show response, then an additional 15 patients will be enrolled for the second stage. Among the 25 patients, If 7 or more patients are able to show response then this treatment regimen will be declared effective. For this decision rule the type I error (declare Mocetinostat promising while it is actually not) rate is 6% and the type II error (declare Mocetinostat not promising while it actually is) rate is around 10%. The early stopping (i.e., stop after the first stage with 10 patients) probability is 0.54 when the true response rate is 15% or lower, and is 0.046 when the response rate is 45% or higher. If a patient died or progressed (and consequently received other treatments) within a year before showing any responses, or provided no information about the best response status, he/she will be recorded as a non-respondent patient. We expect the withdrawal/drop-out rate to be low (around 10%). However if such events occurred due to reasons unrelated with the disease and the patients had not shown any sign of response or progression, such patients will be replaced by new patients.

Due to the potential withdrawal we will enroll totally 56 patients (28 each subtype), and we expect to have 50 analyzable patients (25 each subtype) within 4 years. Note that only the first 25 analyzable patients, for each lymphoma subtype, will be counted towards the analysis of primary objective. For other objectives, all available patients will be used and the analysis will be done separately for each subtype.

Event free survival (defined as time from the date of treatment start to the date of the first documented progressive disease (PD) or death due to any cause) rate using mocetinostat in this selected population will be estimated by the Kaplan-Meier method. For subjects achieving objective response as assessed by investigators, their duration of response is defined as the time from the date of first occurrence of CR or PR whichever is recorded first to the date of the first objectively documented progressive disease (PD) or death due to any cause. The duration of response will be assessed based on the sub-cohort of patients who showed responses also using Kaplan-Meier. To assess the safety and tolerability of mocetinostat, all toxicities related to the treatment will be tabulated and summarized by type and severity for illustration. Adverse events requiring discontinuation of study drug will be summarized and tabulated separately.

Other exploratory objectives include correlation of myc and Bcl-2 positivity with treatment response, assessment of mechanisms of resistance to mocetinostat via information on additional gene sequencing by IMPACT and Foundation Medicine, and analysis of T cell activation and exhaustion in the peripheral blood. For the former, myc and Bcl-2 positivity will be determined by IHC as binary factors which will be correlated with treatment response by Fisher's exact test. The laboratory genetic mutation study will be mostly descriptive for future references. A panel of mutations included in Table 10-2 will be examined for their presence/absence before and after treatments. Analysis of T cell activation and exhaustion will be over 3 timepoints. Due to the expected small sub-sample size, we may only be able to summarize the T cell activation and exhaustion markers measurements. However, if there are >5 responders and >5 non-responders, then Wilcoxon rank sum tests will be used to preliminary assess the correlation between these markers and the response.

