#### Table 9-4. Pericardial Effusion Echocardiographic Assessment and Subject Management Guidelines

 Subjects with ECHO findings of minimal (or trivial) effusion may be discontinued from the study at any time if judged in the subject's best interest, following discussion between the Investigator and the Medical Monitor.

Subjects who are found to have moderate or large pericardial effusions (as defined above) and/or evidence of hemodynamic compromise (regardless of the size of the pericardial effusion) will be immediately removed from study treatment and will be managed according to the accepted standard of care at the discretion of the Investigator. Subjects should be referred to cardiologist for follow up as clinically indicated, until resolution or stabilization.

Subjects who are found to have de novo (i.e. not present at baseline) small pericardial effusions on study will be followed with weekly ECHOs and ECGs for the first month after the new pericardial effusions are first noted or until the effusion has regressed (if sooner). Treatment for the effusion may be administered at the discretion of the Investigator. Study drug will not be discontinued in these subjects, at the discretion of the investigator, unless the effusion progresses.

Subjects presenting with de novo (i.e. not present at baseline) minimal or trivial pericardial effusions visualized by ECHO will be permitted to stay on study treatment since these findings would be considered to represent physiological levels of fluid and typically represents a normal amount of pericardial fluid in a disease-free state. However, such subjects will have increased safety monitoring, including weekly ECHOs and ECGs for 2 weeks to validate the finding as non-pathologic or until the effusion has regressed (if sooner), followed by a return to the regular schedule.

In patients who develop a significant pericardial toxicity, blood will be collected and tested for antinuclear antibody (ANA) and anti-histone antibody testing.

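### The replacement rule in Section 14 can remove dosed patients only if they have no response, and it does not exclude toxicity exits or stable disease, so the primary response rate can be biased upward

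*Combined protocol and SAP*

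**What the plan says.** Section 14.0 sets a Simon two-stage design for each subtype. At stage 1, "in the first stage, we will enroll 10 eligible patients"; 0 or 1 responses stops the cohort. Otherwise 15 more are enrolled, and 7 or more responses among 25 is success. The null rate is 15% and the target 40%.

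The same section handles patients without a response in three steps:

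- A patient who dies or progresses before responding, "or provided no information about the best response status, he/she will be recorded as a non-respondent patient".
- Drop-out is expected to be about 10%. The next sentence, opening with *However*, makes an exception for drop-outs "due to reasons unrelated with the disease and the patients had not shown any sign of response or progression, such patients will be replaced".
- Enrolment is 28 per subtype, and "only the first 25 analyzable patients, for each lymphoma subtype, will be counted towards the analysis of primary objective".

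Section 14 does not mention toxicity in these rules. It does not define *unrelated with the disease* or *analyzable*, or say whether replacement applies to the 10 patients at stage 1.

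Three other sections bear on this. Section 13.1 lists "Unacceptable toxicities" as a ground for withdrawal from the study, separately from progressive disease, and asks a patient who stops treatment "whether she is willing to continue with subsequent follow-up procedures". Section 9.3.4 says patients with certain pericardial findings "will be immediately removed from study treatment". Section 13.2.2 says patients who stop for reasons other than progression, death, new therapy, loss or withdrawn consent "will continue to have radiological tumor assessments per Table 10-1 after end of treatment".

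**The concern.** Drug toxicity is caused by the drug and not by the lymphoma. On plain wording, a patient who leaves because of it, with no response and no progression on record, meets the conditions for replacement. So does a dosed patient with documented stable disease who leaves for a reason other than lymphoma. Section 12.3 makes stable disease a best-response category, and the Section 12.0 endpoint is the proportion with a best response of CR or PR. That patient is a known non-responder, yet can be taken out of the denominator.

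The selection runs one way, because replacement requires no sign of response. A treated patient without a response can be swapped for a new patient; a responder cannot. If the replaced patients would have responded less often than the rest, the tested rate overstates the rate in treated patients, and the chance of calling an inactive regimen effective rises above the stated 6%. With success set at 7 of 25, one or two patients can decide the result. For example, 7 responders with 3 non-responders replaced reads as 7/25 = 28.0%, against 7/28 = 25.0% of all treated.

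**Working it through.** **Inputs (Section 14.0).** Null 0.15; target 0.40; continue if at least 2 of 10 respond; success if at least 7 of 25; drop-out about 10%. The share of patients who would be replaced is not given, so it is varied.

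**The plan's own figures.** With X1 ~ Bin(10, p) and X2 ~ Bin(15, p):

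- P(stop) = P(X1 ≤ 1). At p = 0.15 this is 0.85^10 + 10 × 0.15 × 0.85^9 = 0.1969 + 0.3474 = 0.5443 (stated: 0.54).
- P(success) = Σ over x1 = 2 to 10 of P(X1 = x1) × P(X2 ≥ 7 − x1). At p = 0.15 this is 0.0630 (stated: 6%); at p = 0.40 it is 0.9000 (stated type II error: about 10%).
- Enrolment: 25/(1 − 0.10) = 27.8, so 28.

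The stated design reproduces.

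**Replacement at both looks.** Let d be the share of treated patients replaced and q the response rate they would have had. If the rate in all treated patients is 0.15, the rate among those analysed is (0.15 − d × q)/(1 − d).

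| d | q | Analysed rate | Type I error | Stage-1 stop |
|---|---|---|---|---|
| 0 | – | 0.1500 | 0.0630 | 0.5443 |
| 2% | 0 | 0.1531 | 0.0689 | 0.5331 |
| 5% | 0 | 0.1579 | 0.0789 | 0.5156 |
| 10% | 0 | 0.1667 | 0.0993 | 0.4845 |
| 5% | 0.075 | 0.1539 | 0.0707 | 0.5299 |
| 10% | 0.075 | 0.1583 | 0.0799 | 0.5140 |
| any | 0.15 | 0.1500 | 0.0630 | 0.5443 |

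The 10% row with q = 0 is a ceiling: it needs the plan's whole drop-out allowance to be replaced non-responders. A simulation of that case gave 0.099 with replacement and 0.063 with the same patients scored as non-responders.

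**Replacement in the final 25 only.** Stage 1 uses X1 ~ Bin(10, 0.15). After continuation, K ~ Bin(10 − X1, d/0.85) stage-1 non-responders are replaced, and X2 ~ Bin(15 + K, 0.15/(1 − d)). Type I error is 0.0681, 0.0767 and 0.0933 at d = 2%, 5% and 10% (q = 0), and the stage-1 stop stays at 0.5443.

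**Power if these patients count as non-responders.** If 40% was meant for evaluable patients, the rate in all dosed patients is 0.40 × (1 − d):

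- d = 2%: rate 0.392, power 0.8866
- d = 5%: rate 0.380, power 0.8638
- d = 10%: rate 0.360, power 0.8182

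**The case against.** A reader might infer that Section 14 holds two contradictory rules with no way to choose between them. The text does not support that. *However* makes replacement an exception to the non-responder rule, and a patient who meets its conditions is replaced. The defect is that the exception has no stated boundary for toxicity, and that applying it as written selects one way. Nor do both rules cover the stable-disease patient: such a patient has given best-response information, so only the replacement wording applies.

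The affected group is limited, and this objection largely stands. Section 9.3.4 removes patients from treatment, not from assessment, and Section 13.2.2 keeps them on scans. To be replaced, a patient must also leave follow-up without response or progression. But follow-up ends with new therapy, loss or withdrawn consent, and Section 13.1 lets patients decline it. Exits can also precede any response assessment: Section 3.2.8 reports 73.7% of earlier pericardial SAEs in cycle 1, while the first on-treatment scan is at 8 weeks (Section 10.2).

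The 15% null is itself approximate, and that can matter more. At the DLBCL rate in Table 3-8 (7/41, 17.1%) the rule's false-positive rate is 11.0% with no replacement. At the FL rate (3/28, 10.7%) it is 1.2%, or 2.1% with 10% replaced. This puts the effect in proportion; it does not remove a bias measured against the plan's own null.

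An evaluable-patient analysis can be a legitimate choice if stated in advance. Here the set is not defined, and it can drop a known non-responder.

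**Conclusion.** The point holds as a one-sided replacement rule with an undefined boundary, and it should be corrected. The direction follows from the wording, provided the replaced patients would have responded less often than the rest. The size depends on a share that the documents do not give. From a design value of 6.3%, type I error becomes 6.9% at 2% replaced and 7.9% at 5% if every replaced patient is a non-responder at both looks. It becomes 7.1% at 5% if they would have responded at half the null rate, and does not move if drop-out is unrelated to response. The effect is therefore probably modest.

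Three stronger readings go beyond the documents:

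- That the true type I error is about 10%. The 9.9% figure is a ceiling.
- That patients will be classified case by case to favour the drug. The open-label design and loose wording leave room for this, but nothing shows it is intended.
- That the 15% benchmark is an all-treated rate. Its denominators in Table 3-8 (41 and 28) match the safety counts in Section 3.2.8, which is consistent with that but does not prove it.

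The problem is confined to the primary test. Section 14 uses all available patients for the other objectives and tabulates adverse events that lead to discontinuation.

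**What to change.** In Section 14.0, state that:

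1. Every patient who received mocetinostat counts in the primary denominator, at both the 10-patient and the 25-patient look, with places filled in order of enrolment.
2. Any dosed patient without a documented CR or PR is a non-responder, including toxicity exits and stable disease.
3. Only patients who were never dosed are replaced.
4. *Analyzable* means dosed.

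Limiting replacement to exits unrelated to both disease and drug would not be enough alone: a dosed patient with stable disease could still be removed and a responder could not. If the sponsor keeps that option, it should bar replacement of anyone with a post-baseline response assessment, and report the response rate in all treated patients as a sensitivity analysis.

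The cost is a few sentences, plus one table if the fallback is used. The decision rule is unchanged. The headline rate may be slightly lower. If the 40% target was meant for evaluable patients, power should be restated: about 89%, 86% and 82% if 2%, 5% and 10% of patients are counted as non-responders under this rule.

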### 2.2. SECONDARY OBJECTIVE

- Assess the event free survival of mocetinostat in this selected population
- Assess the duration of response of mocetinostat in this selected population
- Assess the safety and tolerability of mocetinostat in this selected population

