SOCs with the most frequently reported Grade 3/4 AEs ( $\geq$ 10% of all patients for an SOC) across all studies are summarized in Table 3-4; individual events occurring in  $\geq$ 5% of all patients in a preferred term category within those SOCs are also presented.

Overall, the percentage of patients experiencing any Grade 3/4 AE was 81%. The most frequent Grade 3/4 AEs (occurring in  $\geq$ 10% of all patients in a preferred term category) were fatigue (25%), thrombocytopenia (17%), neutropenia (16%), anemia (14%), and febrile neutropenia (12%).

The most frequent Grade 3/4 AEs (occurring in  $\geq$ 5% of all patients in a preferred term category) considered related to study drug were the following: fatigue (23%), neutropenia (14%), thrombocytopenia (14%), anemia (9%), nausea (8%), febrile neutropenia (7%), vomiting (5%), and anorexia (5%).

SOCs with the most frequently reported SAEs ( $\geq 10\%$  of all patients for an SOC) across all studies are summarized in Table 3-4; individual events occurring in  $\geq 5\%$  of all patients in a preferred term category within those SOCs are also presented.

Overall, the percentage of patients experiencing any SAE was 59%. The most frequent SAEs (occurring in  $\geq$ 5% of all patients in a preferred term category) were pneumonia (9%), febrile neutropenia (7%), AML (7%), dehydration (6%), fatigue (6%), and vomiting (5%).

Pericarditis and pericardial effusion, with or without cardiac tamponade, have been reported following treatment with mocetinostat. These events have been associated with SAEs in approximately 4% of patients. The incidence is higher in populations with greater predilection for pericardial abnormalities, including Hodgkin lymphoma, but also AML and NHL. Bladder toxicity resulting in dysuria and rarely hemorrhagic cystitis has been described in a few patients receiving mocetinostat.

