### 11.0 TOXICITIES/SIDE EFFECTS

#### 11.1. Adverse events

#### 11.1.1. Definitions and reporting

An adverse event is defined as the appearance of (or worsening of any pre-existing) undesirable sign(s), symptom(s), or medical condition(s) that occur after patient's signed informed consent has been obtained. Abnormal laboratory values or test results occurring after informed consent constitute adverse events only if they induce clinical signs or symptoms, are considered clinically significant, require therapy (e.g. hematologic abnormality that requires transfusion or hematological stem cell support), or require changes in study medication(s).

Adverse events that begin or worsen after informed consent should be recorded in CRDB. Conditions that were already present at the time of informed consent should be recorded in the Medical History in CRDB. Adverse event monitoring should be continued for at least 30 days following the last dose of study treatment. Adverse events (including lab abnormalities that constitute AEs) should be described using a diagnosis whenever possible, rather than individual underlying signs and symptoms. When a clear diagnosis cannot be identified, each sign or symptom should be reported as a separate Adverse Event.

Adverse events will be assessed according to the Common Terminology Criteria for Adverse Events (CTCAE) version 4.03. If CTCAE grading does not exist for an adverse event, the severity of mild, moderate, severe, and life-threatening, corresponding to Grades 1 - 4, will be used. CTCAE Grade 5

(death) will not be used in this study; rather, information about deaths will be collected though a Death form.

The occurrence of adverse events should be sought by non-directive questioning of the patient (subject) during the screening process after signing informed consent and at each visit during the study. Adverse events also may be detected when they are volunteered by the patient (subject) during the screening process or between visits, or through physical examination, laboratory test, or other assessments. As far as possible, each adverse event should be evaluated to determine:

1. The severity grade (CTCAE Grade 1-4)

2. Its duration (Start and end dates)

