### 17.3 Serious Adverse Event (SAE) Reporting

An adverse event is considered serious if it results in ANY of the following outcomes:

- Death
- A life-threatening adverse event
- An adverse event that results in inpatient hospitalization or prolongation of existing hospitalization
- A persistent or significant incapacity or substantial disruption of the ability to conduct normal life functions
- A congenital anomaly/birth defect

 Important Medical Events (IME) that may not result in death, be life threatening, or require hospitalization may be considered serious when, based upon medical judgment, they may jeopardize the patient or subject and may require medical or surgical intervention to prevent one of the outcomes listed in this definition

Note: Hospital admission for a planned procedure/disease treatment is not considered an SAE.

SAE reporting is required as soon as the participant signs consent. SAE reporting is required for 30-days after the participant's last investigational treatment or intervention. Any events that occur after the 30-day period and that are at least possibly related to protocol treatment must be reported.

If an SAE requires submission to the IRB office per IRB SOP RR-408 'Reporting of Serious Adverse Events', the SAE report must be sent to the IRB within 5 calendar days of the event. The IRB requires a Clinical Research Database (CRDB) SAE report be submitted electronically to the SAE Office as follows:

For IND/IDE trials: Reports that include a Grade 5 SAE should be sent to [contact]. All other reports should be sent to [contact].

For all other trials: Reports that include a Grade 5 SAE should be sent to [contact]. All other reports should be sent to [contact].

The report should contain the following information:

Fields populated from CRDB:

- Subject's initials
- Medical record number
- Disease/histology (if applicable)
- Protocol number and title

Data needing to be entered:

- The date the adverse event occurred
- The adverse event
- The grade of the event
- Relationship of the adverse event to the treatment (drug, device, or intervention)
- If the AE was expected
- The severity of the AE
- The intervention
- Detailed text that includes the following
  - A explanation of how the AE was handled
  - $\circ$  A description of the subject's condition
  - Indication if the subject remains on the study
- If an amendment will need to be made to the protocol and/or consent form

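### The main safety table is limited to events judged treatment-related, no all-cause adverse event, SAE or death summary is planned, and the Grade 5 rules conflict

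*Combined protocol and SAP*

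**What the plan says.** Section 2.2 makes safety a secondary objective: "Assess the safety and tolerability of mocetinostat in this selected population". Section 14.0 gives its analysis in two sentences. The first is the main summary: "all toxicities related to the treatment will be tabulated and summarized by type and severity for illustration". The second adds a table with no stated relatedness condition: "Adverse events requiring discontinuation of study drug will be summarized and tabulated separately". The analysis set is also defined there: "For other objectives, all available patients will be used and the analysis will be done separately for each subtype". That means up to 28 patients per subtype and 56 in all.

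Collection is wider than analysis. Section 11.1.1 has adverse events that begin or worsen after consent entered in CRDB, each with a yes/no relatedness call and an outcome that can be fatal. Section 11.2 requires SAEs to be reported whatever the suspected cause, apart from listed exemptions. Section 11.3 does the same for pericardial findings.

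On fatal events, Section 11.1.1 limits severity to Grades 1 to 4 and says of Grade 5: "death) will not be used in this study; rather, information about deaths will be collected though a Death form". Section 17.3 nevertheless contains the instruction "Reports that include a Grade 5 SAE should be sent to" followed by an address.

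**The concern.** The main safety table depends on a causality call. With no control arm and no blinding, there is no background rate against which to judge those calls. They are hardest for events that relapsed lymphoma or earlier treatment can also cause, such as cytopenias, fever, infection and effusions. An event judged unrelated that does not stop treatment appears in neither planned table. Examples are an episode of febrile neutropenia, an anemia, or a minimal or small pericardial effusion.

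Febrile neutropenia is the clearest case. Section 11.2.1 does not count admission purely for its evaluation and treatment as an SAE. An unrelated episode that led only to such an admission, met no other seriousness criterion and did not stop the drug would therefore be missing from the SAE counts as well.

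The Grade 5 wording is a second, smaller gap. If grades stop at 4, a table by severity cannot show that a toxicity was fatal, and no other summary of deaths is specified.

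What is at stake is how fully the report answers a secondary objective. The primary endpoint is not affected.

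**Working it through.** **1. Inputs.** Section 3.2.8 (Human safety and tolerability data) gives grade 3/4 rates both for all causes and for related events. The table of grade 3/4 events (the first of two numbered 3-4) gives all-cause counts with N=435. The related rates are whole percentages only.

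**2. Reproducing the stated figures.** Febrile neutropenia 52/435 = 12.0%; anemia 59/435 = 13.6%; thrombocytopenia 72/435 = 16.6%; neutropenia 69/435 = 15.9%; fatigue 108/435 = 24.8%. All match the table.

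**3. Share of affected patients removed by the filter.** The formula is (all-cause % − related %) / all-cause %. The range lets the rounded related figure vary by ±0.5 points.

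| Grade 3/4 event | All-cause | Related | Share removed | Range | Expected in 56, all-cause vs related |
|---|---|---|---|---|---|
| Febrile neutropenia | 12.0% | 7% | 5.0/12.0 = 42% | 38–46% | 6.7 vs 3.9 |
| Anemia | 13.6% | 9% | 4.6/13.6 = 34% | 30–38% | 7.6 vs 5.0 |
| Thrombocytopenia | 16.6% | 14% | 2.6/16.6 = 16% | 13–19% | 9.3 vs 7.8 |
| Neutropenia | 15.9% | 14% | 1.9/15.9 = 12% | 9–15% | 8.9 vs 7.8 |
| Fatigue | 24.8% | 23% | 1.8/24.8 = 7% | 5–9% | 13.9 vs 12.9 |

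The last column is 56 × rate, for example 56 × 0.120 = 6.7 and 56 × 0.07 = 3.9. Within one subtype of 28, febrile neutropenia would be 28 × 0.120 = 3.4 versus 28 × 0.07 = 2.0.

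**4. All grades.** From the same section, constipation and pyrexia each fall from 25% to 12% (13/25 = 52% removed) and peripheral edema from 20% to 10% (50%). Nausea falls only from 71% to 66% (5/71 = 7%). The effect of the filter depends strongly on the event.

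**5. Which events the two tables miss.**
- Related events enter the first table.
- Events that stop the drug enter the second, whatever their cause.
- Unrelated events that do not stop the drug enter neither.

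Under Section 9.3.4 and Table 9-4, moderate or large effusions and hemodynamic compromise lead to removal from study treatment with no attribution condition, so they would reach the second table. New minimal or small effusions can remain on treatment, so they reach a table only if judged related or if the drug is stopped.

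**6. Fatal events.** Section 11.1.1 grades 1 to 4, sends deaths to a separate form and allows a fatal outcome code. Section 17.3 presumes that Grade 5 reports exist. The two cannot both describe the grading scale, and Section 14.0 names no output for deaths.

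**The case against.** The strongest reply is that the information exists and only the planned display is narrow. Adverse events are recorded without a causality limit, SAEs are reported regardless of cause, and institutional monitoring applies, so all-cause tables could be produced at reporting. That is correct. It confines the point to the planned summary, but a table that could be produced is not one the plan commits to.

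Several stronger readings are tempting, and the documents do not support them.

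- *Only related events are tabulated.* The discontinuation table carries no relatedness condition.
- *Serious pericardial events would disappear.* The larger effusions and hemodynamic compromise require removal from treatment and so would be tabulated. All pericardial findings are also reported regardless of relationship (Section 11.3).
- *Deaths are lost.* They are captured on a Death form, as a fatal outcome, and as events in event-free survival. They are also SAEs unless due to documented progression. What is missing is a listing and a severity level.
- *The trial will under-report harm.* Neither data collection nor SAE reporting is restricted to related events.

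Two further replies have force. A related-event rate and an all-cause rate are different quantities, and the all-cause rate includes disease effects. The case is therefore for showing both, and not that the related rate is a biased estimate of itself. Also, Section 10.3 says laboratory data will be summarized by CTCAE grade. That might show low blood counts whatever their cause, but it specifies no table and would not show febrile neutropenia as an event, infections or effusions.

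Finally, the Section 17.3 text is generic routing language that also covers other trials and defines no analysis. It still contradicts Section 11.1.1 on whether Grade 5 is used.

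**Conclusion.** The point holds as a gap in the planned safety summary. Adverse events judged unrelated that do not stop treatment appear in neither adverse event table, no all-cause adverse event, SAE or death summary is specified, and a fatal toxicity has no severity level.

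In the protocol's own pooled data, the related-only filter removes between about 7% (fatigue) and 42% (febrile neutropenia) of affected patients among the five most frequent grade 3/4 events. The direction is certain, because patients with a related event are a subset of those with any such event. The size in this trial is not.

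The 435 patients include 177 with MDS, AML or other leukemia and only 80 with NHL (Table 3-7), and some received mocetinostat with azacitidine, gemcitabine or docetaxel. Section 3.2.6 itself says that neutropenia and thrombocytopenia vary with diagnosis and with myelosuppressive partners. The expected counts assume that the pooled rates carry over and that both subtypes reach 28 patients. They are illustrations, not forecasts.

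The change should be made: it concerns a secondary objective and is inexpensive.

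**What to change.** 1. Amend Section 14.0 so that all adverse events and all SAEs from first dose to 30 days after last dose are tabulated by type and worst grade, regardless of attribution and by subtype, with treatment-related events as a subset. Keep the discontinuation table. The all-cause adverse event table is needed as well as the SAE table, because admissions purely for febrile neutropenia are not counted as SAEs.
2. Add a listing of deaths by cause and relatedness.
3. Reconcile Sections 11.1.1 and 17.3 on whether Grade 5 is used, so that the severity table has a defined place for fatal events and agrees with the SAE reports.

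The cost is one additional set of tables and a short text amendment. The adverse events and their relatedness calls already go into CRDB and deaths are already collected, so no new data are needed. Sample size and the primary analysis do not change.
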